6. STUDY PROCEDURES

6.1. Study Period

6.1.1. Baseline/Day 0 Visit (at ANC clinic/center)

Baseline/Day 0 – Pre Assessment of Study Eligibility

After informed consent is obtained, the subject must have the following procedures performed prior to the start of therapy:

- Medical history;
- Obstetrical history;
- Urine pregnancy test (if not done at any prior ANC visit for this pregnancy);
- Concomitant treatment history;
- Rapid diagnostic test for *P. falciparum* (eg, Binax, See Appendix 1);

- Complete physical examination;
- Oral Temperature;
- Routine obstetric checkup;
- Obstetrical ultrasound (if urine pregnancy test positive);
- Thick and thin peripheral blood smears for parasite identification and counts (2 smears per subject) in subjects with Rapid Diagnostic Test positive for *P. falciparum*;
- Hemoglobin level (with HemoCue™);
- Urine analysis for glucose and proteins;
- A dried blood blot for molecular genotyping (reinfection vs. recrudescence, eg, MSP1/MSP2) of parasite and for genetic markers of CQ resistance (eg, PfCRT);
- Two predose blood samples (one for AZ and one for CQ and desethyl-CQ analyses) from the subjects who consented for PK analysis (See Section 7.3 Pharmacokinetic Assessments). The exact date and time of blood sample collection will be recorded.

Day 0 – Post Assessment of Eligibility

Subjects who have met all inclusion/exclusion requirements will have the following procedures performed:

- Administer treatment (AZCQ);
- Assess adverse events;
- Distribute LLINs.

6.1.2. Days 1 Home Visit (by the field worker)

- Assess adverse events;
- Concomitant treatment history;
- Oral temperature: will be taken by the fieldworker;
- If a subject presents with symptoms of malaria (fever $>37.5^{\circ}\text{C}$, oral), no further AZCQ dose would be given. The subject would be immediately referred to the investigator for parasite counts and appropriate treatment for malaria in pregnancy as per national/ local guidelines;

- Administer treatment: second dose of AZCQ will be administered at home under supervision by the fieldworker(s);
- Confirm that the LLINs has been installed in the home of the subject.

6.1.3. Days 2 Visit (at ANC clinic/center)

- Assess adverse events;
- Concomitant treatment history;
- Oral temperature;
- If a subject presents with symptoms of malaria (fever $>37.5^{\circ}\text{C}$, oral), no further AZCQ dose would be given. The subject would be immediately referred to the investigator for parasite counts and appropriate treatment for malaria in pregnancy as per national/ local guidelines;
- Administer treatment: third dose of AZCQ;
- Two blood samples (one for AZ and one for CQ and desethyl-CQ analyses) from the subjects who consented for PK analysis at each of the following timepoints: predose, 2 hours (as close to 2 hours as possible) and 8 hours (window: 4 to 12 hours). The exact date and time of blood sample collection will be recorded.

6.1.4. Follow-up Visits on Days 7, 14, 21, 28, 35, 42 at ANC clinic/center)

- Assess adverse events;
- Concomitant treatment history;
- Limited physical examination (only on Days 42);
- Oral temperature;
- Hemoglobin (with HemoCueTM) (only on Day 42);
- Thick and thin peripheral blood smears for parasite identification and counts (2 smears at each visit);
- If a subject presents with symptoms of malaria (fever $>37.5^{\circ}\text{C}$, oral), and has parasitemia (microscopy), she will receive standard antimalarial treatment according to the local treatment guidelines for malaria in pregnancy;
- A dried blood blot will be collected at each visit for potential molecular testings;

- Two blood samples (one for AZ and one for CQ and desethyl-CQ analyses) on Days 7 and 14 (a random time point) from the subjects who consented for PK analysis. The exact date and time of blood sample collection will be recorded;
- One blood sample (for CQ and desethyl-CQ analyses only) on Days 21 and 28 (a random time point) from subjects who consented for PK analysis. The exact date and time of blood sample collection will be recorded.

6.1.5. Unscheduled Visits through Day 42

Any subject who develops signs and symptoms of malaria (fever ($>37.5^{\circ}\text{C}$, oral) and new signs and symptoms of malaria including malaise, headache or abdominal pain at any time other than the scheduled visits through Day 42, will be required to report to the investigator/study staff immediately for further evaluation. Blood smears and blood blots will be collected. The subject will be treated with the current standard of care for malaria in pregnancy.

In the event that subjects require an unscheduled visit (eg, for additional follow up due to any safety concerns, concomitant illness etc), the following assessments/procedures should be completed at a minimum:

- Symptom-directed physical exam with temperature;
- Adverse event assessment;
- Concomitant treatment history.

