9.2.1. Analysis of Primary Endpoint

The proportion of subjects with parasitological response (PCR corrected) at Day 28 post first dose of study medication will be estimated for the primary endpoint using the MITT and PP subject populations. The proportion will be estimated from the Kaplan-Meier curve based on the time to the first occurrence of parasitological failure (PCR corrected). Use of the Kaplan-Meier curve/product limit estimator is recommended by WHO⁸ and has been used in analyzing primary efficacy endpoints in late stage antimalarial treatment clinical trials.⁹²⁻⁹⁴

A subject will be a parasitological responder if she has a zero parasite count on the Day 7 visit without subsequent recrudescence (PCR corrected) through the day of consideration, otherwise she is a parasitological failure. In addition, subjects who withdraw from the study treatment during the first three days due to development of malaria symptoms and are administered antimalarial standard of care treatment for malaria in pregnancy, will be considered parasitological failures. The time (number of days) to the first occurrence of parasitological failure will be the analysis variable. The time in days is defined as [date of the parasitological failure event – date of the first dose of study medication + 1].

Subjects who do not experience the defined event (parasitological failure) will be censored as follows:

- Subjects who withdraw from the study early due to any reason will be censored on the day of the last available blood smear measurement;
- Subjects who continue on in the study but have all remaining blood smears missing from a given point in time onward will be censored on the day of the last available smear;
- Subjects completing the Day 42 visit post first dose of study medication will be censored on the day of the last available blood smear measurement;
- Subjects receiving any concomitant antimalarial for reinfection (PCR corrected) or in the absence of parasitemia will be censored at the visit date if the antimalarial is given after collection of the blood smear on that day. Otherwise the subject will be censored on the day of the last available previous blood smear measurement;
- Subjects who are lost to follow-up without any follow-up blood smears will have a censored duration of 1 day.

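### Sections 6.1.4 and 6.1.5 set different conditions for antimalarial treatment during follow-up, and neither covers smear-positive women without fever; this is mainly a care gap, with a small effect on the Day 28 estimate

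*Protocol*

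**What the plan says.** **Scheduled visits, Days 7 to 42 (Section 6.1.4).** Smears are taken at each visit. If a woman presents with malaria symptoms, specified as oral fever above 37.5°C, "and has parasitemia (microscopy), she will receive standard antimalarial treatment according to the local treatment guidelines for malaria in pregnancy". Fever and a positive smear are both required.

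**Unscheduled visits through Day 42 (Section 6.1.5).** The section applies to a woman with fever and "new signs and symptoms of malaria including malaise, headache or abdominal pain at any time other than the scheduled visits through Day 42". She reports for further evaluation, and smears and blots are collected. Then: "The subject will be treated with the current standard of care for malaria in pregnancy". The smear result is not stated as a condition.

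**Dosing days (Sections 6.1.2 and 6.1.3).** With fever, "no further AZCQ dose would be given", and the woman is "immediately referred to the investigator for parasite counts and appropriate treatment for malaria in pregnancy".

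**Primary analysis (Section 9.2.1).** A responder has a zero count at Day 7 and no PCR-confirmed recrudescence afterwards; fever plays no part. On treatment during follow-up: "Subjects receiving any concomitant antimalarial for reinfection (PCR corrected) or in the absence of parasitemia will be censored at the visit date", provided the antimalarial came after that day's smear. Otherwise censoring goes back to the previous smear. Separately, "subjects who withdraw from the study treatment during the first three days due to development of malaria symptoms" and who receive standard antimalarial treatment count as failures.

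**The concern.** The same state on Days 7 to 42 falls under different instructions depending on whether the visit was scheduled. Because Section 9.2.1 makes censoring depend on whether an antimalarial was given, the difference carries into the Kaplan-Meier estimate.

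The larger matter is what both sections omit. Inclusion criterion 2 requires asymptomatic parasitaemia, so recurrence without fever is foreseeable, and it is the state that the endpoint counts as failure or reinfection. No Day 7 to 42 instruction addresses it. Sections 3 and 4.4 place the return to standard antenatal care with IPTp after the Day 42 evaluation. Section 1.2 names clearance of asymptomatic parasitaemia as a primary objective of IPTp and placental infection as a particular concern for the fetus. Sites would have to decide for themselves what to do for these women, and those decisions would in turn determine which reinfections are censored.

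**Working it through.** The plan gives no figure on this point. The check compares the text and then sizes the effect under stated assumptions.

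**1. The text side by side**

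| State, Days 7 to 42 | Scheduled visit (6.1.4) | Unscheduled visit (6.1.5) | Consequence in 9.2.1 |
|---|---|---|---|
| Fever, new symptoms, smear negative | Not covered by the treatment rule | Treated, as written | Censored if treated; otherwise stays at risk |
| Fever, new symptoms, smear positive | Treated | Treated | Failure if recrudescence; censored if reinfection |
| No fever, smear positive, recrudescence | No action stated | Not within the trigger | Failure, treated or not |
| No fever, smear positive, reinfection | No action stated | Not within the trigger | Censored only if treated |

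The sections conflict in the first row. The care gap is in the last two rows. The primary estimate depends on treatment practice only in the first and last rows.

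**2. How many women might have any recurrence by Day 28**

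Section 1.5.2.2 gives PCR-uncorrected efficacy of 95% and 99% in the two African adult treatment studies: 166 × 0.05 = 8.3 and 166 × 0.01 = 1.7 women. The chloroquine-alone arm in pregnant women in Ghana (Section 1.4.2.2) had 30% uncorrected failure: 166 × 0.30 = 49.8. These count all recurrences, with or without fever, and the last comes from a different regimen.

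**3. First row: censoring symptomatic smear-negative women**

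Inputs: 166 enrolled less 10% dropout (Section 9.1) gives about 149. Assumed: 7 recrudescences, with 1, 2, 2 and 2 at Days 7, 14, 21 and 28.

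- Base: 148/149 × 146/148 × 144/146 × 142/144 = 142/149 = 95.3%, Greenwood half-width 3.4 points.
- With k further women censored at the Day 7 smear: 148/149 × (142 − k)/(148 − k).
- k = 1, 3, 5, 10 gives 95.3, 95.2, 95.2, 95.0%. The largest shift is about 0.3 points.

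This takes the censored women to have average risk. If all k would have recrudesced by Day 28, the uncensored estimate would be (142 − k)/149: 94.6% at k = 1 and 88.6% at k = 10. The documents give no evidence for so extreme a case.

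**4. Last row: reinfections censored only if treated**

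Assume constant hazards to Day 28, a for recrudescence and b for reinfection. Assume also that no reinfection is treated and that recrudescence is never detected after one. Then:

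- failure with reinfected women kept at risk = a/(a + b) × [1 − exp(−(a + b))];
- failure with reinfection censored = 1 − exp(−a);
- overstatement of response = the second minus the first.

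The Ghana arm gives the documented reinfection figure, 11/208 = 5.3%, with 21 of 208 undetermined, and 14% recrudescence. The 5% recrudescence figure matches the 95% response in Section 9.1.

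- 5% and 5%: a = b = 0.0513; 0.5 × (1 − 0.9025) = 0.0488; 0.0500 − 0.0488 = about 0.12 points.
- 14% and 5.3%: a = 0.1508, b = 0.0545; 0.7347 × 0.1856 = 0.1364; 0.1400 − 0.1364 = about 0.37 points.
- Assumed 20% reinfection: 0.51 points (5% recrudescence) and 1.42 points (14%).

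For scale, the half-width at 95% with 149 women is 1.96 × √(0.95 × 0.05/149) = 3.5 points.

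**The case against.** Section 6.1.5 mentions further evaluation, smears and standard of care, so a site might treat only on a positive smear. Section 6.1.4 does not forbid treating a smear-negative woman. Section 5.5 allows medication that is not contraindicated, and Section 9.2.1 provides for antimalarials given without parasitaemia. All of this narrows the practical difference. It does not remove it: one section states the smear condition and the other does not.

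Keeping an untreated reinfected woman at risk is also a coherent choice. Section 7.1 says that reinfection is not treatment failure, and blots are collected at every visit through Day 42, so a later recrudescence can still be found. PCR-uncorrected results are a planned secondary analysis. This stands, and it is why the figures in step 4 are upper bounds. It does not explain why the choice should depend on whether an antimalarial happened to be given.

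A reader might infer that Days 1 and 2 add a third, fever-only rescue rule that also drives censoring. The text does not support that. Fever then stops dosing and leads to parasite counts, no smear is scheduled on those days, and treatment for malaria symptoms in the dosing period is classed as failure. A reader might also infer that any febrile smear-negative woman is censored if she comes unscheduled; Section 6.1.5 requires new signs or symptoms as well.

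**Conclusion.** The point holds as an inconsistency between Sections 6.1.4 and 6.1.5, together with an unstated action for afebrile parasitaemia through Day 42. It is first a matter of patient care and of consistent conduct across sites.

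The effect on the primary estimate is real but small: at most about 0.3 points from censoring up to 10 symptomatic smear-negative women, assuming average risk, and at most about 0.1 to 0.4 points from treatment-dependent censoring of reinfections at about 5% reinfection. Larger values need higher assumed reinfection rates and complete masking. It might be inferred that the Day 28 response is materially biased or that afebrile recrudescences escape the analysis. Neither follows: the bounds lie well inside the 3.5-point half-width, and recrudescence is an event whatever the fever or treatment.

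**What to change.** Reconcile Section 6.1.4 with Section 6.1.5, and both with Section 9.2.1, so that the same state is handled consistently on Days 7 to 42 whatever the type of visit. State how smear-positive women without fever are handled in that period. The clinical content belongs to the investigators and local guidelines; the request is only that the passages agree and leave no state unaddressed. Days 1 and 2 need no extra smears.

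In Section 9.2.1, censor at the smear date of the first PCR-confirmed reinfection whether or not an antimalarial was given, or report this as a sensitivity analysis. The estimate then no longer depends on who treated which reinfection.

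The cost is wording in two procedure sub-sections and one censoring rule, with no added visits or women. Slightly fewer women remain at risk after reinfection. Section 9 says that major changes to the primary analysis go into a protocol amendment, so if the primary rule is changed, the protocol is the place to do it.

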6.1.6. Safety Follow-up Visit for EIU Assessment

Every attempt should be made to follow up the subject following delivery or at termination of pregnancy for EIU safety assessment. In case of no associated serious adverse events (SAE), subjects should be followed up by fieldworkers at clinic or at home within 14 calendar days after expected date of delivery or termination of pregnancy.

A. Following data will be collected at this visit:

- Concomitant treatment history;
- Maternal information and delivery: any history of complications during pregnancy, at and after delivery, eg, pre-eclampsia, hemorrhage, infection, etc;
- Neonatal Information (See Section 7.2 for details):
 - Outcome of pregnancy;
 - Outcome of infant.

When feasible and relevant for the assessment of the case (eg, in case of neonatal malformation/anomalies, premature delivery, low birth weight neonates, developmental assessment, kernicterus, or any other neonatal illness, hospitalization, drug therapy etc), further follow-up of neonates should continue until the information is satisfactory or the outcome has been established or the condition has stabilized.

B. In the event of an elective termination, spontaneous abortion, and late fetal death, following details should be recorded if available:

- Reason for termination;
- Gestational age at termination;
- Results of physical examination (gender, external anomalies) and pathology.

Any additional tests, procedures, treatments, and consultations may be conducted if recommended by local/national ANC guidelines and deemed clinically indicated by the investigator.

Any serious adverse events (SAEs) occurred after the informed consent through one month after the delivery or the termination of pregnancy should be reported to the study doctors immediately. Refer to Section 8.2 for details.

6.2. Subject Withdrawal

Subjects may withdraw from the study at any time at their own request, or they may be withdrawn at any time at the discretion of the investigator or sponsor for safety, behavioral, or administrative reasons. If a subject does not return for a scheduled visit, every effort should be made to contact the subject. In any circumstance, every effort should be made to document subject outcome and pregnancy outcome, if possible. The investigator should inquire about the reason for withdrawal, request the subject to return all unused investigational product(s), request the subject to return for a final visit, if applicable, and follow-up with the subject regarding any unresolved adverse events.

If the subject withdraws from the study and also withdraws consent for disclosure of future information, no further evaluations should be performed and no additional data should be collected. The sponsor may retain and continue to use any data collected before such withdrawal of consent.

Unless a subject withdraws the consent or leaves the town/village, she should continue in the study for follow up visits through Day 42, and following delivery or termination of pregnancy for EIU safety assessment. Subject may be withdrawn from the study treatment (during the first three days) due to safety concerns (eg, adverse events, significant laboratory abnormalities, and contraindications of concomitant medications), but not from the clinical study per se unless the subject withdraws consent. The standard antenatal care including IPTp will be given to the subject per local ANC guideline. The circumstances and data surrounding these events should be clearly documented in the case report form. The

investigator must determine the primary reason for discontinuation. A discontinuation must be reported immediately to the Pfizer medical monitor or his/her designated representative if it is due to a serious adverse event (SAE).

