8.9. Exposure During Pregnancy

This is a study exclusively in pregnant women participants. Enrolled subjects will be asymptomatic pregnant women who will receive study drugs for preventive treatment of malaria. Since this is the first time AZ and CQ combination will be administered to pregnant women, all subjects will be followed up for EIU safety assessments following delivery or termination of pregnancy. The reason(s) for an induced abortion should be specified. All pregnancy-related AEs through Day 42 following the first dose of AZCQ and the pregnancy outcomes will be recorded on CRF pages as required clinical study data. Since all the information generally included on an EIU form will be collected on CRF paper, a separate EIU form is not required.

090177e1811d3ccb\Approved\Approved On: 19-Feb-2010 20:59

If the outcome of the pregnancy meets the criteria for immediate classification as a serious adverse event (ie, spontaneous abortion, stillbirth, neonatal death, or congenital anomaly [including that in an aborted fetus, stillbirth or neonatal death]), the investigator should follow the procedures for reporting serious adverse events.

In the case of a live birth, the “normality” of the newborn can be assessed at the time of birth (ie, no minimum follow-up period of a presumably normal infant is required before an Exposure in Utero Form can be completed). The “normality” of an aborted fetus can be assessed by gross visual inspection, unless pre-abortion test findings are suggestive of a congenital anomaly.

Additional information about pregnancy outcomes that are classified as serious adverse events follows:

- “Spontaneous abortion” includes miscarriage and missed abortion.
- All neonatal deaths that occur within 1 month of birth should be reported, without regard to causality, as serious adverse events. In addition, any infant death after 1 month that the investigator assesses as possibly related to the exposure during pregnancy to the investigational medication should be reported.

Additional information regarding the EIU may be requested by the investigator. Further follow-up of birth outcomes will be handled on a case-by-case basis (eg, follow-up on preterm infants to identify developmental delays). In the case of paternal exposure, the investigator must obtain permission from the subject’s partner in order to conduct any follow-up or collect any information.

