8.10. Withdrawal Due to Adverse Events (See also Section on Subject Withdrawal)

Withdrawal due to adverse event should be distinguished from withdrawal due to insufficient response, according to the definition of adverse event noted earlier, and recorded on the appropriate adverse event CRF page.

When a subject withdraws due to a serious adverse event, the serious adverse event must be reported in accordance with the reporting requirements defined below.

Unless a subject withdraws consent or leaves the town/village, she may be withdrawn from the study treatment but should continue in the study as we must follow them up for pregnancy outcome.

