14. SPONSOR DISCONTINUATION CRITERIA

Premature termination of this study may occur because of a regulatory authority decision, change in opinion of the IRB/IEC, drug safety problems, or at the discretion of Pfizer. In addition, Pfizer retains the right to discontinue development of AZCQ at any time.

If a study is prematurely terminated or discontinued, Pfizer will promptly notify the investigator. After notification, the investigator must contact all participating subjects and the hospital pharmacy (if applicable) within 30 days. As directed by Pfizer, all study materials must be collected and all CRFs completed to the greatest extent possible.

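### Sections 6.2 and 8.10 except women who leave the town or village from exposure-in-utero follow-up, contradicting the protocol's duty to document pregnancy outcome for every subject

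*Protocol*

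**What the plan says.** **The exception.** Section 6.2: "Unless a subject withdraws the consent or leaves the town/village, she should continue in the study for follow up visits through Day 42". The same sentence goes on to name the EIU assessment after delivery or pregnancy termination. Section 8.10, on withdrawal for adverse events: "Unless a subject withdraws consent or leaves the town/village, she may be withdrawn from the study treatment but should continue in the study". That sentence closes by giving pregnancy outcome as the reason for staying in.

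**The duty without an exception.** Section 8.9, citing first use of the combination in pregnancy, says that "all subjects will be followed up for EIU safety assessments following delivery or termination of pregnancy". Section 6.1.6: "Every attempt should be made to follow up the subject following delivery or at termination of pregnancy for EIU safety assessment". Footnotes b and l of the Schedule of Activities and Section 7.2 say much the same, and none of them mentions place of residence.

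**Section 6.2 against itself.** Earlier in the section: "In any circumstance, every effort should be made to document subject outcome and pregnancy outcome, if possible". Just after the exception, women may be taken off treatment in the first three days "but not from the clinical study per se unless the subject withdraws consent".

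**Early termination.** Section 14 lists drug safety problems among the grounds for stopping. It requires the investigator to contact all participating subjects within 30 days, and adds: "As directed by Pfizer, all study materials must be collected and all CRFs completed to the greatest extent possible". It does not mention EIU outcomes.

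**The concern.** EIU assessment is a named safety endpoint in Section 2.2, and every participant is pregnant when dosed. Withdrawal of consent gives an ethical reason to stop collecting data, and Section 6.2 already deals with it separately, including withdrawal of consent for disclosure of future information. Moving house gives no such reason. It only makes follow-up harder.

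Two sites could therefore treat the same woman differently. One would trace her, relying on Sections 6.1.6 and 8.9. The other would close her record, relying on Section 6.2 or 8.10. The only EIU route described is a fieldworker seeing the woman at the clinic or at home, so the protocol names no method for reaching someone who has gone elsewhere. What is at stake is the completeness of the pregnancy-outcome table. With a single arm there is no comparison group to share the loss, so any gap falls directly on the reported rate.

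**Working it through.** This is a reading of text, so the passages are tested first. The arithmetic only indicates scale.

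**Can the passages be reconciled as they stand?**

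1. *The exception covers visits and the general duty covers outcomes.* This fails, because the sentence in Section 6.2 that carries the exception names the EIU assessment as well as the visits to Day 42.
2. *The duty that applies in any circumstance overrides the exception.* This is possible. But that duty is general and limited to what is possible, while the exception is specific and comes after it. A site could reasonably treat the specific text as governing.
3. *Only withdrawn consent ends participation.* The Section 6.2 sentence saying so concerns women taken off study treatment in the first three days. Section 8.10 deals with women taken off treatment for adverse events and lists two exceptions. For an overlapping group, one section gives one way out and the other gives two.

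The text is contradictory, and no section says which passage prevails.

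**Time during which a woman could move**

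- Gestation at entry: 14 to 30 weeks (Section 4.1). Day 42 is 6 weeks later.
- Gestation at Day 42: 14 + 6 = 20 weeks to 30 + 6 = 36 weeks.
- Delivery at 40 weeks (assumption): 40 − 36 = 4 weeks to 40 − 20 = 20 weeks.
- Delivery at 37 weeks instead: 1 to 17 weeks.

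The Schedule of Activities shows no visit between Day 42 and the EIU contact.

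**Loss rate**

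The protocol gives none for pregnancy outcomes. Its only figure is 10% dropout in Section 9.1, which belongs to the sample size for the primary efficacy endpoint:

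- (z₀.₉₇₅ + z₀.₈₀)² × p(1 − p) / w² = 7.849 × 0.95 × 0.05 / 0.05² = 149.1
- 149.1 / 0.90 = 165.7, rounded up to the stated 166

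The 10% is therefore borrowed below as an illustration only.

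**Effect on the observed rate (illustration; none of these inputs is in the protocol)**

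Let p be the true adverse-outcome rate, L the share of women lost, and k the rate in lost women divided by the rate in retained women. Then p = (1 − L)·o + L·k·o, so the observed rate is o = p / (1 − L + L·k). With p = 5%:

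- L = 10%, k = 1: 0.05 / 1.00 = 5.0%
- L = 10%, k = 2: 0.05 / 1.10 = 4.5%
- L = 10%, k = 3: 0.05 / 1.20 = 4.2%
- L = 20%, k = 3: 0.05 / 1.40 = 3.6%
- L = 10%, k = 0.5: 0.05 / 0.95 = 5.3%

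For L from 5% to 20% and k from 1 to 3, the observed rate lies between 5.0% and 3.6%. If women who move are at lower risk, the error runs the other way.

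**Effect on precision when k = 1**

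There is no bias, only fewer women. With zero events, the one-sided 95% upper bound is 1 − 0.05^(1/n): 1.79% for n = 166 and 1.99% for n = 149 (10% lost).

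**The case against.** The strongest reply is that the protocol never tells sites to abandon pregnancy outcomes. Section 6.2 asks for every effort to document them in any circumstance and to contact anyone who misses a visit, and several other sections require EIU follow-up without qualification. Section 4.4 encourages women to stay in the area and deliver in hospital. This stands to the extent that the wording is not a clean release. It does not remove the contradiction, because the exception is explicit and appears twice.

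The second reply is that serious outcomes are captured anyway. SAEs are defined for mother or fetus (Section 8.5). Spontaneous abortion, stillbirth, neonatal death and congenital anomaly are SAEs (Section 8.9). Reporting runs to one month after delivery or termination if that is later (Section 8.2), and Section 8.12.1 anticipates a subject treated elsewhere. This stands, so it would be wrong to call the EIU visit the only source of fetal safety data. SAE reporting is still not a full substitute. Preterm birth alone is not on the Section 8.9 list, and SAE reports do not confirm normal outcomes, which the denominator of a rate needs.

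The third reply is that Section 14 is merely silent. It requires contact with all participating subjects and CRF completion as far as possible, and Section 8.9 places pregnancy outcomes on the CRF as required data. This stands: the section does not end follow-up.

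The consequence is also limited. The safety tables are descriptive, and the primary endpoint does not depend on EIU completeness.

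**Conclusion.** The point holds as an internal contradiction that should be resolved. Sections 6.2 and 8.10 except women who move from continuing in the study, and Section 6.2 includes the EIU assessment. Other sections, and Section 6.2 itself, require pregnancy outcome to be pursued for all. The exposed period is about 4 to 20 weeks per woman if delivery is at 40 weeks. The likely effect is an incomplete descriptive rate. Any bias depends on assumed loss and relative risk; in the illustration it runs from none to 5.0% being observed as 3.6%.

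A reader might infer more, and the documents do not support it:

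- *That fetal outcomes are lost selectively.* The protocol gives no rate of moving away and no link between moving and outcome. Selective loss is a possibility, not a finding.
- *That referral elsewhere for a complication, or travel to deliver, counts as leaving.* Section 6.2 does not mention either.
- *That a safety stop would end pregnancy follow-up.* Section 14 does not say so. It is a secondary point of clarification.

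**What to change.** 1. In Sections 6.2 and 8.10, delete leaving the town or village as an exception to EIU follow-up, so that only withdrawal of consent for disclosure of future information ends it.
2. For women who move, allow the pregnancy and infant outcome to be obtained remotely, by telephone, from a relative or from the delivering facility, using contact details taken at Day 0.
3. As a secondary clarification, state in Section 14 whether EIU outcome collection for women already dosed continues after early termination, consistent with Sections 8.2 and 8.9.

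The cost is a few sentences, a contact sheet at Day 0 and some tracing effort. Outcomes obtained remotely will carry less detail than those from a visit. Dosing, endpoints and sample size do not change.
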